8.1 Investigator Training

(1) Organize training related to the clinical study of the observational device and participate in the clinical study of the medical device within the scope authorized by the principal investigator; (2) Fully understand and comply with clinical study protocols and relevant laws and regulations and responsibilities related to clinical research of observational device.

8.2 Data Management

All data inputs are in Chinese. eCRF shall be completed during or as soon as possible after each visit and updated at any time to reflect patient status updates. The data shall be reviewed by the investigators to ensure the accuracy and authenticity of all data entered the eCRF. If any evaluation is not performed during the trial or any information is unavailable, inapplicable, or unknown, the investigators shall record it in the eCRF. The investigators shall electronically sign the verified data.

8.3 Setting Clinical Events Committee

The Clinical Events Committee (CEC) is a group of independent experts, who is responsible for reviewing and adjudicating adverse events in the study, to ensure that the judgment of adverse events in clinical research meets the requirements of the protocol.

The CEC committee will be composed of independent clinical experts with experience or expertise in neurosurgery, and who are not involved in this study. The CEC will provide the definition and evaluation criteria of the adverse events in accordance with the CEC charter and this protocol, and review and adjudicate the specific events reported.

9 Ethical Considerations and Informed Consent of Clinical Study

9.1 Ethical Considerations

The clinical study must be conducted in accordance with the *Declaration of Helsinki*, and appropriate regulations and laws. The clinical study protocol shall be approved by the ethics committee (EC) of the leading site before conducting the study.

The investigators need to submit the protocol, ICF (If any), and other related documents through the management department of the clinical research institution to the EC before the initiation of the study. The clinical study will be conducted after approved by the EC. Any modification on the protocol shall be approved by the EC before implementation.

Clinical research institutions for medical devices shall meticulously maintain clinical research records and foundational documents in compliance with applicable laws and regulations.

9.2 Patient Inform Consent Process

This study is a retrospective study and does not involve the informed consent of patients, and an ICF waiver will be applied to the ethics committee. If necessary, an informed consent process will be performed as required by the Ethics Committee.

10 Adverse Event, Serious Adverse Event

10.1 Adverse Event

10.1.1 Definition

An Adverse Event (AE) is any untoward medical occurrence during the clinical study, whether or not related to observational devices (from *Good Clinical Practice for Medical Devices*).

10.1.2 Determination of Severity

According to following criteria, severity of AEs can be categorized as mild, moderate, and severe.

- Mild: Transient or mild discomfort; no limitation in activity; no medical intervention/therapy required.
- Moderate: Marked limitation in activity, assistance usually required; medical intervention / therapy required, possible hospitalization.
- Severe: Extreme limitation in activity, significant assistance required; significant medical intervention/therapy required, hospitalization or probable hospice care.

10.1.3 Determination of Causality Relationship Between AEs and Devices AE

The causality relationship of AEs with medical devices included "definitely related", "possibly related", "likely unrelated" and "definitely unrelated". "Definitely related" and "possibly related" are judged as related to the observational device; "likely unrelated" and "definitely unrelated" are judged as unrelated to the observational device. The specific judgment criteria are as follows:

Related to the observational device: (1) There is a reasonable temporal relationship between the AE and the observational device; (2) The AE is consistent with the known hazard of the device or may be explained by the mechanism of the observational device; (3) The harm is alleviated or disappears after the use of the device is stopped; (4) The harm occurs again after the use of the device is resumed; (5) The AE cannot be explained by other reasons. It is judged as "definitely related" if all five criteria are met and as "possibly related" if two of them are met.

Unrelated to the observational device: (1) There is no reasonable temporal relationship between the AE and the observational device; (2) The AE is a type of event that is unlikely to be caused by the observational device; (3) The AE can be explained by concomitant device(s)/drugs, patient disease progression, and other therapeutic effects. It is judged as "definitely unrelated" if all three criteria are met and as "likely unrelated" if one of them is met.

The severity of adverse events and their relevance to devices or procedures will be determined independently by the CEC Committee in accordance with the unified regulations and principles, combined with the collection data (the collection data collection includes patient medical records, laboratory tests, and, if necessary, patient's imaging data.) to make a judgment.

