2.2.2 Principle of Operation and Mode of Action

The observation device is a flow diverter (FD) designed for permanent implantation into the lumen of the aneurysm or vascular dissection to carry the aneurysm. The approach site is usually an angiography-guided femoral artery. Neurovascular access is obtained according to standard endovascular maneuvers. This can be achieved by navigating the guidewire to the location of the aneurysm neck or to the target location, and then the microcatheter is navigated through the guidewire. After removing the guidewire, select the appropriate size flow guide according to the instructions for use (IFU). The instrument is assembled inside a coil and placed in a sterile area. The device (implant/delivery pusher/introduction sheath) is removed from the coil as a whole. The blood flow guide was inspected and prepared according to the IFU. Follow the "Instructions for Use" in the IFU to push the FRED implant into the microcatheter by pushing the delivery guidewire. By delivering a guidewire, the implant can advance further through the microcatheter until it reaches the distal tip of the microcatheter, but not beyond the microcatheter tip (proximal fluorescent labeling on the FRED delivery system can aid in this process). At this point, fluoroscopy must begin. While the implant remains within the microcatheter, it is positioned and deployed by aligning its distal radiopaque end marker. Once the position has been determined under fluoroscopy, the microcatheter is retracted and the delivery guidewire is advanced to allow the FRED implant to unfold in the aneurysm neck. If the implant is not fully deployed, it can be retracted and repositioned if necessary. Once deployed, the implant expands and clings to the wall of the blood vessel and across the neck of the aneurysm.

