2.3.3 Mode and Duration of Contact with Human Body

Prolonged and continuous blood contact (>30 days).

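### After final deployment of a permanent implant, the causality rule in Section 10.1.3 makes *definitely related* effectively unattainable and gives no literal grade to an event that meets three criteria

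*Protocol*

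**What the plan says.** Section 10.1.3 of the protocol uses four causality grades: definitely related, possibly related, likely unrelated and definitely unrelated. The first two count as related and the last two as unrelated.

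Relatedness rests on five criteria. In summary, they are:

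1. plausible timing;
2. a known hazard of the device, or a mechanism that could explain the event;
3. abatement, worded as "3) The harm is alleviated or disappears after the use of the device is stopped";
4. recurrence, worded as "4) The harm occurs again after the use of the device is resumed";
5. no other explanation.

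The grading rule is "It is judged as 'definitely related' if all five criteria are met and as 'possibly related' if two of them are met". It has no proviso for a criterion that cannot be assessed.

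The device is described in Section 2.2.2 as "designed for permanent implantation into the lumen of the aneurysm". Section 2.3.3 gives continuous blood contact of more than 30 days, and Section 2.3.6 says single use. Retrieval is described only within the procedure. Section 2.2.2 says "If the implant is not fully deployed, it can be retracted and repositioned if necessary", and Section 4.4.2(4) describes re-sheathing followed by re-deployment or complete removal.

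Relationship to the device is assessed for strokes and deaths (Section 4.4.1) and causality is recorded for all adverse events (Section 10.1.4). Section 8.3 has the CEC work to its charter and to this protocol. Under Section 11, only the CEC's determinations enter the analysis of the safety endpoints.

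**The concern.** Criteria 3 and 4 describe withdrawing an exposure and giving it again. That fits a product whose use can be interrupted. Once a flow diverter is in its final position, its use does not stop, so there is nothing to resume. Because *definitely related* requires every criterion, these two control access to the top grade.

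The study objective (Section 3) is long-term safety, so the events of most interest, such as later stroke, delayed rupture, stent thrombosis and death, occur mostly after final deployment. If none of them can reach the top grade, a low or zero count there reflects the rule and says nothing about the device. A reader of a post-market safety report could take it as reassurance. Within the related events, a stent thrombosis with plausible timing, a recognised mechanism and no other cause would get at best the same grade as an event that meets only two criteria.

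**Working it through.** No sample size, power or error rate is involved, and the plan gives no figure to reproduce. The check is a count of what the rule can return.

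**Inputs.** The five criteria and the grading rule come from Section 10.1.3. The permanence of the implant comes from Sections 2.2.2, 2.3.3 and 2.3.6. The limits on retrieval come from Sections 2.2.2 and 4.4.2(4).

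**Step 1: which criteria can be met after final deployment.** Criteria 1, 2 and 5 can. Criterion 3 needs use to stop and criterion 4 needs it to resume, and the protocol describes neither after full deployment. A death cannot meet criterion 3 in any case. The maximum is therefore 3 of 5, against 5 of 5 required.

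**Step 2: enumerate the patterns.** Three criteria, each met or not met, give 2^3 = 8 patterns. The number with k criteria met is C(3,k): 1, 3, 3 and 1 for k = 0, 1, 2 and 3.

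| Criteria met (of 1, 2, 5) | Patterns | Rule read literally | Two read as at least two | With the change proposed below |
|---|---|---|---|---|
| 0 or 1 | 1 + 3 = 4 | not graded related | not graded related | not graded related |
| 2 | 3 | possibly related | possibly related | possibly related |
| 3 | 1 | no grade stated | possibly related | definitely related |

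These are counts of logical patterns and do not forecast how often each will occur.

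**Step 3: read off the results.**

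- *Definitely related* is reached by 0 of 8 patterns under either reading of the current rule.
- The strongest attainable pattern, with criteria 1, 2 and 5 all met, has no literal grade, because the rule names only five and two.
- Related in total: 3 of 8 patterns read literally, 3 + 1 = 4 of 8 if two means at least two, and 3 + 1 = 4 of 8 after the change. The pooled split therefore stays the same under the at-least-two reading.

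**Step 4: look for an exception.** During the procedure the device can be retrieved and deployed again, and the treatment column of Table 4-3 collects adverse events. A transient event that eased on retrieval and returned on re-deployment could meet criteria 3 and 4. It would still have to meet 1, 2 and 5 to be graded definitely related.

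**The case against.** The strongest case on the other side has four parts.

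**The category is not strictly empty.** A reader might infer that the top grade is empty by construction and its count fixed at zero. The documents do not support that, because Sections 2.2.2 and 4.4.2(4) allow retrieval and re-deployment, and procedural complications are in scope under Section 4.4.1(4). This stands. The defect is confined to events after final deployment, where the grade is effectively unattainable.

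**No endpoint uses the split between definite and possible.** Stroke rate, mortality, symptom rate, complication rate and the occurrence of adverse events are all defined without it, and both grades count as related. This also stands. A reader might infer that the device-related total is understated. That would follow only if the CEC left events meeting three criteria ungraded, and reading two as a minimum is natural. Events also remain identifiable by name, severity and outcome (Section 10.1.4), so a stent thrombosis is not hidden. Only its causality grade is uninformative.

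**The report may not tabulate four grades.** The protocol does not say that it will, so a published zero cannot be asserted as a certainty. The grades will still be assigned and recorded.

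**The CEC may exercise judgement.** Its charter is not at hand and may deal with criteria that do not apply. But Section 8.3 binds the CEC to this protocol as well, so a charter that relaxed the all-five rule would contradict Section 10.1.3. The wording needs correcting in either case.

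**Conclusion.** The concern holds for events after final deployment. At most 3 of the 5 required criteria can be met, so *definitely related* is effectively unattainable for the long-term events the study is meant to assess. An event meeting exactly three criteria has no literal grade.

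The consequence is limited. Endpoint rates do not change, and the related/unrelated split does not change provided two is read as at least two. The harm is to the four-level grading, which cannot distinguish clear device-caused events from weak associations. How many events this affects cannot be estimated, because the protocol gives no event rates.

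The conclusion assumes that stopping use means removing or withdrawing the device, and that this does not happen after full deployment. The protocol describes retrieval only during the procedure, which supports both assumptions.

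**What to change.** In Section 10.1.3, and in the same words in the CEC charter:

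- Mark criteria 3 and 4 as not applicable after final deployment. Keep them for events where retrieval or re-deployment makes them observable; deleting them would discard that evidence.
- Define *definitely related* as all applicable criteria met. After final deployment these are criteria 1, 2 and 5.
- Define *possibly related* as at least two applicable criteria met, but not all. This also closes the gap at three and four criteria.
- Have the CEC record which criteria it judged applicable for each event.

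The cost is a wording change to the protocol and charter, with ethics committee approval as Section 12 requires. Any event already graded under the present rule would need regrading so that the stage analyses in Section 5.4 share one scale. The downside for the sponsor is that some events may now be reported as definitely related, which is less favourable to the device. Clinical management is not affected.

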4.4 Endpoint

4.4.1 Safety Endpoint

(1) Stroke Rate

Definition: The stroke rate refers to the proportion of stroke patients in the total number of patients.

Collection Content: Record the date of stroke, type (ischemic or hemorrhagic), severity (mild, moderate, severe), location and cause, treatments, or other interventions for stroke, and whether the

stroke resulted in the patient's death. Also assess the relationship of the stroke event to the observational device and the patient's concurrent antithrombotic therapy. All stroke events are assessed by the CEC.

(2) All-cause Mortality

Definition: Mortality refers to the proportion of dead patients in the total number of patients.

Collection Content: Record the date of the death event and whether it was neurogenic. Evaluate the relationship of the death event to the observational device. Neurogenic death is defined as a death event directly resulted from a neurologic cause judged by the Clinical Event Committee (CEC).

(3) Lesion-Related Symptoms or Signs Rate

Definition: Lesion-related symptoms or signs rate refers to the proportion of patients with lesion-related symptoms or signs to total patients.

Collection Content: All neurological related symptoms which were not present at baseline or worsened from baseline will be record including headache, hemiplegic paralysis, seizure, aphasia, stroke, bleeding (including intracerebral, subarachnoid hemorrhage, retroperitoneal, others), facial nerve pain, seizures, vision loss, aphasia, hemiplegia, oculomotor nerve palsy, neck pain or stiffness, loss of consciousness, meningeal irritation, pre-retinal hemorrhage, increased intracranial pressure, other aneurysm-related symptoms, or abnormal signs (list specific symptoms or abnormal signs).

(4) Lesion-Related Complication Rate

Definition: Lesion-related complication refers to the proportion of patients with lesion-related complication to total patients.

Collection Content: Record whether the following complications occurred during the procedure. Principal Investigator (PI) shall evaluate the relationship between complications and observational device, other interventional devices, and surgical procedures.

- Complications of arterial puncture: including puncture site pain, puncture site local bleeding, injury to the puncture artery or adjacent nerves,;
- Dissection or perforation of the parent artery,
- Rupture or perforation of the aneurysm,
- Vasospasm;
- Stent thrombosis,
- Other complication

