10.1.4 Reporting and Follow-up

The investigators shall record all AEs that occur during the study, including the name, start and end

dates, severity, causality relationship with the device, and outcome of each AE, as well as any action taken for each AE.

The investigators shall provide symptomatic treatment and follow-up for each AE until all symptoms disappear or become stable, or otherwise there is another reasonable explanation.

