10.2.2 Reporting of SAEs

For SAEs, investigators shall conduct a comprehensive analysis and assessment of the SAE immediately after becoming aware of it, including its severity and relationship to the observational device. For suspected SAE related with medical device, investigators shall report to relevant personnel. For SAEs lead to death or SAEs lead to serious injury, reports must be submitted within reported within the prescribed time frame.

11 Clinical Event Committee

The Independent Clinical Event Committee (CEC) will evaluate safety endpoints data and the sponsor will appoint a CEC composed of physicians (not investigators) to rule uniformly adjudicate all SAE and/or AEs associated with the observational device or observational procedure identified. Only CEC's determinations of the collected data (Data collection includes patient medical records, laboratory tests, and, if necessary, patients' imaging data) were used for the analysis of safety endpoints.

12 Protocol Amendments

If there is any modification to the protocol after EC approval, a "protocol revision statement" or revised protocol is required, which shall be signed and confirmed by the sponsor and the coordinating investigator and approved by the EC before implementation.

13 Direct Access to Source Data and Documentation

Source data refers to the original records of clinical findings, observations, and other activities in a medical device clinical study, as well as all information in certified copies, which can be used for the reconstruction and evaluation of the clinical study.

Source documents refer to printed documents, visual files, or electronic files that contain source data.

The archived materials for this clinical study include: (1) clinical study protocol; (2) electronic case report forms (eCRFs); (3) informed consent forms (If any); (4) original medical records of the patients; (5) statistical analysis reports; (6) all other materials such as interim reports and final summary reports of the clinical study.

Investigators must carefully complete all study documents, including the confirmation of all participated patients (effectively verifying different records, such as eCRFs and original hospital records), all original signed informed consent forms of patients (if any), and detailed records in all eCRFs. After the study is completed, all clinical study documents shall be submitted to the clinical research institution for safekeeping.

14 Clinical Study Report

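### The causality rules in Section 10.1.3 can grade one adverse event as both related and unrelated to the device, and the protocol states no precedence

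*Protocol*

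**What the plan says.** Protocol Section 10.1.3 defines four grades of relation to the device and folds them into two.

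- **Related list, five criteria:** plausible timing (1), fit with a known hazard or the device mechanism (2), relief once use stops (3), return once use resumes (4), no other explanation (5). The threshold is: "It is judged as 'definitely related' if all five criteria are met and as 'possibly related' if two of them are met". Both grades count as related.
- **Unrelated list, three criteria:** implausible timing (1), a type of event the device is unlikely to cause (2), and another cause (3): "The AE can be explained by concomitant device(s)/drugs, patient disease progression, and other therapeutic effects". The threshold is: "It is judged as 'definitely unrelated' if all three criteria are met and as 'likely unrelated' if one of them is met". For the split, "likely unrelated' and 'definitely unrelated' are judged as unrelated to the observational device".

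The grades are used in several places. Under Section 10.1.4 investigators record, among other items, the "causality relationship with the device, and outcome of each AE". Section 4.4.1(1) says of strokes: "Also assess the relationship of the stroke event to the observational device". Section 4.4.1(2) asks the same of deaths. On adjudication, Section 8.3 says: "The CEC will provide the definition and evaluation criteria of the adverse events in accordance with the CEC charter and this protocol". Under Section 11 only the CEC's determinations "were used for the analysis of safety endpoints".

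**The concern.** The two lists are scored separately, and meeting a threshold on one does not exclude meeting the threshold on the other. An event can therefore fall on both sides of the protocol's own related/unrelated split. Section 10.1.3 does not say which list is applied first or which result prevails, and no other section does.

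This is a stated rule with two opposite answers, rather than a detail left for later. Two graders who follow the text faithfully can classify the same event differently. Data are analysed in three stages (Section 5.4), so an unwritten convention could also differ between stages.

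At stake is the device-relatedness classification of AEs, SAEs, strokes and deaths, in a post-market study meant to describe the long-term safety of this device. There may also be an effect upstream. Section 10.2.2 asks investigators to report SAEs suspected to be device-related. Section 11 can be read as sending AEs to the CEC according to their association with the device or procedure.

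**Working it through.** The protocol gives no figure to reproduce, so the check is one of logic.

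**Inputs (Section 10.1.3).** R1 to R5 are the related criteria and U1 to U3 the unrelated ones, each 1 if met and 0 if not. Let r = R1+R2+R3+R4+R5 and u = U1+U2+U3. The related threshold is r = 2 or r ≥ 2, depending on how *two* is read. The unrelated threshold is u = 1 or u ≥ 1. The *definitely* grades need r = 5 or u = 3.

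**Assumptions.** Section 2.2.2 describes a permanent implant, so R3 and R4 are set to 0. The paired criteria are treated as strict opposites, which favours the protocol because it minimises overlap: U1 = 1−R1, U2 = 1−R2, U3 = 1−R5. This leaves 2³ = 8 patterns.

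| R1, R2, R5 | r | u | Read as at least | Read as exactly |
|---|---|---|---|---|
| 1, 1, 1 | 3 | 0 | possibly related | no grade |
| 1, 1, 0 | 2 | 1 | **both** | **both** |
| 1, 0, 1 | 2 | 1 | **both** | **both** |
| 0, 1, 1 | 2 | 1 | **both** | **both** |
| 1, 0, 0 | 1 | 2 | likely unrelated | no grade |
| 0, 1, 0 | 1 | 2 | likely unrelated | no grade |
| 0, 0, 1 | 1 | 2 | likely unrelated | no grade |
| 0, 0, 0 | 0 | 3 | definitely unrelated | definitely unrelated |

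**Result.** Three of 8 patterns are both *possibly related* and *likely unrelated* on either reading. The second row is the ordinary one: plausible timing, a known hazard, and another possible cause. The protocol itself expects such cases, since Section 4.4.1(1) asks how each stroke relates both to the device and to concurrent antithrombotic therapy. The other two rows are less usual.

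**Effect of precedence (at-least reading).** If the related list prevails, 1 + 3 = 4 of 8 patterns are related. If the unrelated list prevails, 1 of 8 is.

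**Relaxing the pairing.** Suppose an event may meet neither R2 nor U2, and neither R5 nor U3. There are then 2 × 3 × 3 = 18 patterns. The same 3 are doubly graded. On the at-least reading, 1 gets no grade: plausible timing only, with r = 1 and u = 0.

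**The *definitely* grades.** If R3 and R4 were the only related criteria met, then r = 2 and u = 3: *possibly related* and *definitely unrelated* together. This is unlikely for an implant left in place, but it shows that a precedence rule must cover all four grades.

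**Search for a tie-break.** Section 10.1.3 closes by having the CEC judge by unified principles, without stating an order. Section 4.6 refers to the CEC bylaws, and Section 8.3 to the charter and to this protocol. Section 4.4.1(5) points to Section 11 for causality, but Section 11 holds no criteria. Section 10.1.3 is therefore the protocol's only causality rule.

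**The case against.** The strongest defence is that relatedness is decided by an independent committee using judgment, not by a tally. The provisions for that judgment sit in a charter that is not shown, and only the CEC's results enter the safety analysis. It therefore cannot be shown from the protocol that any event would end up with two grades. Further, no endpoint is defined as a device-related rate, the study is descriptive (Section 5.3.2), and it has no success criterion (Section 5.6).

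This limits the severity but does not remove the point. Section 8.3 ties the CEC to the protocol as well as to its charter, and investigators must grade every AE under the same text. A tie-break in the charter would leave the protocol giving two answers.

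A reader might infer three stronger things that the documents do not support:

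- *Most events are ambiguous.* If all five related criteria may vary freely, 22 of 32 patterns get both sides on the at-least reading, or 16 of 24 if return is allowed only after relief. These counts rest on stopping and resuming use, which hardly applies to a permanent implant, and patterns are not event frequencies.
- *The best-supported device events go ungraded.* The no-grade rows need *two* to mean exactly two, so that a third supporting criterion would remove the grade. That is a strained reading of a graded scale. It justifies clearer wording and no more.
- *The safety rates are unreliable.* Stroke, mortality and overall AE/SAE rates count patients or events without regard to relatedness.

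**Conclusion.** The point holds: Section 10.1.3 can give one event two opposite classifications, and the protocol does not resolve them. This does not depend on how the thresholds are read or on loose pairing of the criteria. One ordinary pattern and two less usual ones are affected, out of 8 under the stated assumptions. The protocol offers no basis for saying how many real events that represents.

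The consequence is confined to the device-relatedness classification of AEs, SAEs, strokes and deaths and, as Sections 10.2.2 and 11 are worded, possibly to which SAEs are reported as suspected device-related and which AEs reach adjudication. The reporting effect is uncertain, because reporting rests on suspicion rather than on the graded split. Severity is minor to moderate.

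**What to change.** In Section 10.1.3:

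1. Write *at least two* and *at least one* for the middle grades.
2. State one precedence between the lists, covering the *definitely* grades, so that each event gets exactly one grade. One example is that an event meeting at least two related criteria is judged related even if another explanation exists. That example would also override *definitely unrelated* when only criteria 3 and 4 are met, so the text should say whether this is intended. The sponsor and the CEC may choose another rule, provided it is single and fixed before further events are graded.
3. Name a single grade for events meeting neither threshold.
4. State how related criteria 3 and 4 apply to a permanent implant. This may move some events across the split: an event meeting criteria 1 and 3 scores two if criterion 3 can count, and one if it cannot.

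Align the CEC charter with the result and re-check events already graded.

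The cost is a short paragraph, matching charter text and the re-check. The downside of the example precedence is that the related count may be somewhat higher.
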